11.0 BIOSTATISTICS

This project involves a parallel-arm randomized controlled clinical trial to compare the efficacy of three psychotherapy interventions: 1) Individual Meaning-Centered Psychotherapy (IMCP); 2) Supportive Individual Psychotherapy (ISP); and 3) Enhanced Usual Care arm (EUC). We plan to recruit altogether 414 patients (138 in each arm) with solid tumors with advanced disease. The primary outcomes include assessments of meaning (LAP-R), spiritual well-being (FACIT-Sp) and psychological distress (HADS, SAHD, HAI, MQOL).

Omnibus MANOVA for the primary aim:

The general paradigm for assessing the outcomes will be multivariate analysis of variance (MANOVA). MANOVA is appropriate because the primary psychosocial outcomes are highly correlated. The MANOVA method essentially combines the multiple dependent variables together into a weighted linear combination of canonical variates. The canonical coefficients provide the weights in this linear combination. The canonical weights have several advantages. The main advantage is that they inform the relative contribution of each outcome to the overall canonical function (i.e., whether or not meaning contributes more than spiritual well-being to the overall canonical function). MANOVA was chosen, rather than, for example, a mixed-effects modeling approach, primarily because of these considerations. In MANOVA, the combined canonical variate is analyzed in a manner similar to a univariate ANOVA.

The primary aim of this study will be evaluated in one omnibus, one-way MANOVA model against the null hypothesis that all three randomized arms entail comparable post-intervention outcomes in meaning, spiritual well-being, and psychological distress. Thus, the dependent variables will be the six primary outcome assessments (LAP-R, FACIT-Sp, HADS, SAHD, HAI, and MQOL) measured at the post-intervention time point (week 7). The sole independent variable is the randomized intervention assignment. Dunlop, Cortina, Vaslow & Burke (1996) showed that this method provides the most generalizable findings, findings that do not depend on the patients' baseline scores or other baseline characteristics. Thus, the omnibus MANOVA will test whether or not the psychotherapy groups differ in all six correlated outcomes of interest.

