Analyses: Putative explanatory covariates will be identified and tested statistically using the method originally described by Baron and Kenny (1986), and more recently by MacKinnon (2008). Specifically, these will involve Multi-Variate Analysis of Covariance (MANCOVA) using the changes in the six primary outcomes (post intervention minus baseline) as a function of intervention condition, controlling as covariates the effects of gender, race/ethnicity, and baseline covariates in religiosity, social support, optimism, physical symptom burden, pain severity, and overall symptom burden. This analytic approach entails the following advantages: 1) change scores have the advantage of clearly identifiable direction of change, 2) psychosocial outcomes are measured on an interval scale (such as measures of temperature in the Fahrenheit or Celsius scales), so that change scores are less prone to problems associated with respondents using different internal psychological scales; and 3) precedence exists (Flay et al. 1995) in interventions designed for behavioral change. This method offers several advantages, both in terms of power as well as interpretation, to a traditional repeated measures design for analyzing data when both independent and dependent variables are assessed at two or more time points (Huck & McLean, 1975; Willet, 1988-9). Change score analyses will include the baseline score as a covariate if change is significantly correlated with baseline score (as is often the case).

To assess the relative impact of Individual Meaning-Centered Psychotherapy on different aspects of meaning (e.g., purpose, coherence, existential vacuum), as well as on different aspects of spiritual well-being (meaning versus faith):

Two additional MANOVA models will be carried out. In the first model, pre-post change scores of different aspects of meaning (e.g., purpose, coherence, existential vacuum) will be modeled by intervention conditions to examine the relative impact of IMCP on these outcomes. The canonical weights will be used to estimate the relative contribution of each mean components on the overall canonical function. Components of spiritual well-being will also be analyzed similarly, in a separate MANOVA model. Univariate ANOVA contrasts will be used to compare IMCP against ISP and IMCP against EUC.

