include estimating missing data, complete data analysis, and intention to treat analysis. Although missing data can be estimated using a number of powerful techniques (Graham, Hofer, Donaldson, MacKinnon & Schafer, 1997), we intend to use a multiple imputation procedure described by Schafer and Olsen (1997), which is capable of handling categorical data, continuous data, and any combination of the two. Graham et al. (1997) have argued that parameter estimates using this method are unbiased and have standard errors that are typically only slightly larger than those generated by other methods. In order to assess the effect of this imputation method, we will compare results based on imputed data to those based only on subjects who completed the study (this comparison allows for an assessment of the extent to which biases may have influenced study results). Finally, we can analyze data assuming that those subjects who dropped out of treatment had no change in either meaning or psychological distress.

Procedures to control False Discovery Rate (FDR):

One final issue is that of multiple statistical analyses. While the use of MANOVA models decreases the possibility of inflated type I error normally observed when several outcome measures are being evaluated, analysis of the individual dependent variables can also incorporate a multiple comparisons method, such as a the False Discovery Rate-controlling procedure (Benjamini & Hochberg, 1995).

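### Canonical weights are the planned measure of IMCP's relative impact on components of meaning and spiritual well-being, but they are partial coefficients and can distort or reverse the sign of a component's effect when outcomes are highly correlated

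*Combined protocol and SAP*

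**What the plan says.** All the relevant text is in section 11.0 of the combined protocol and SAP.

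- **Primary aim.** The subsection on the omnibus MANOVA names as the main advantage of canonical weights that "they inform the relative contribution of each outcome to the overall canonical function", with meaning against spiritual well-being as the example. It adds that "MANOVA was chosen, rather than, for example, a mixed-effects modeling approach, primarily because of these considerations". It also states that "MANOVA is appropriate because the primary psychosocial outcomes are highly correlated". The omnibus model has six outcomes and three arms.
- **Second secondary aim.** Pre-post change scores on aspects of meaning "will be modeled by intervention conditions to examine the relative impact of IMCP on these outcomes". The estimator is named next: "The canonical weights will be used to estimate the relative contribution of each mean components on the overall canonical function". Then: "Components of spiritual well-being will also be analyzed similarly, in a separate MANOVA model". The paragraph ends: "Univariate ANOVA contrasts will be used to compare IMCP against ISP and IMCP against EUC".
- **Multiplicity.** The closing subsection on the false discovery rate (FDR) says that "analysis of the individual dependent variables can also incorporate a multiple comparisons method", which is optional wording.

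The section gives no correlations among outcomes. It does not mention standardizing the weights or reporting structure coefficients, and it has no rule for the second canonical function.

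**The concern.** The secondary aim asks which components IMCP moves most. The weights answer a different question: how much each component adds to separating the arms once the other components are held fixed. With uncorrelated components the two questions have the same answer. As correlation rises, a component can improve clearly and still get a small or negative weight because a neighbouring component carries the same information.

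Three arms add a second difficulty. Two canonical functions are possible, and the first points in the direction in which the arms differ most. That direction may be both therapies against EUC rather than anything specific to IMCP.

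At stake is a published statement that IMCP works mainly through one component, or does little for another, resting on a number that does not measure this.

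**Working it through.** **Plan's own figures.** The document gives no figure for the weights. Its only computed output in this area is the G*Power result, which reproduces from its stated inputs: noncentrality 104 × 0.20 = 20.8, Pillai V = 0.20/1.20 = 0.1667, critical F 2.9936 on 6 and 97 degrees of freedom, power 0.8063. It does not use the weights, so this point leaves it unchanged. Whether its inputs match the text is a separate matter.

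**Inputs.** From the document: six primary outcomes, three arms, 104 per arm at post-intervention, and within-IMCP pilot effects (Table 1, pre to post) of 1.01 for Meaning/Peace and 0.66 for Faith. Assumed: all other effects and every correlation. All outcomes are coded so that higher is better.

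**Step 1: two components, one contrast.** The weights are w = S⁻¹d. With unit variances and correlation r:

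- w1 = (d1 − r·d2)/(1 − r²)
- w2 = (d2 − r·d1)/(1 − r²)

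So w2 is negative whenever d2/d1 < r. The pilot effects serve only as an illustration, since they are within-arm changes and not arm contrasts.

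- r = 0.6: w1 = (1.01 − 0.396)/0.64 = 0.96; w2 = (0.66 − 0.606)/0.64 = 0.08. The effect ratio is about 1.5 to 1; the weight ratio is about 11 to 1.
- r = 0.7: w1 = (1.01 − 0.462)/0.51 = 1.07; w2 = (0.66 − 0.707)/0.51 = −0.09.
- The sign changes at r = 0.66/1.01 = 0.65.

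Smaller effects behave the same way. Effects of 0.5 and 0.4 at r = 0.8 give 0.50 and 0.00. Effects of 0.4 and 0.25 at r = 0.7 give 0.44 and −0.06.

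**Step 2: three components.** Take effects 0.5, 0.5, 0.4, with correlation 0.8 between the first two and 0.3 otherwise. By symmetry the first two share a weight a, and the third has weight c:

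- 1.8a + 0.3c = 0.5
- 0.6a + c = 0.4

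The solution is a = 0.235, c = 0.259. The smallest effect gets the largest weight.

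**Step 3: sampling, three arms of 104.** There were 3,000 simulated trials per case, ISP's advantage over EUC was half of IMCP's, and all pairs had correlation r. The largest-effect figures compare ranking by first-function weight with ranking by the univariate IMCP−EUC difference.

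| Effects vs EUC | r | At least one negative weight | Largest effect named: weights | Largest effect named: univariate |
|---|---|---|---|---|
| 0.5, 0.3 | 0.3 | 14% | 88% | 88% |
| | 0.5 | 36% | 92% | 93% |
| | 0.7 | 68% | 96% | 97% |
| 0.5, 0.4, 0.3 | 0.3 | 31% | 68% | 70% |
| | 0.5 | 61% | 71% | 73% |
| | 0.7 | 88% | 76% | 80% |

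Every component truly improves in these cases. Negative structure coefficients appear in only about 2 to 3% of the same trials.

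**Step 4: which contrast the first function describes.** Six outcomes, r = 0.4, effects relative to EUC.

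- *Case A:* both therapies 0.4 on four outcomes; IMCP 0.3 and ISP 0 on LAP-R and FACIT-Sp. The first function gives LAP-R and FACIT-Sp −0.46 and the other four 0.44. It places ISP 0.70 from EUC and IMCP 0.43, although IMCP is at least as good on all six.
- *Case B:* ISP 0.4 on all six; IMCP 0.7 on LAP-R and FACIT-Sp and 0.4 on the rest. The weights are 0.58, 0.58 and 0.02 four times. IMCP is 0.84 from EUC and ISP 0.49. The arms are ordered sensibly, but four outcomes with a true 0.4 SD benefit appear to contribute almost nothing.

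**The case against.** A reader might infer that the relative-impact answer will be wrong. The documents do not support that, for four reasons.

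- **Order is often kept.** For two positively affected components and one contrast, w1 − w2 = (d1 − d2)/(1 − r) and w1 + w2 = (d1 + d2)/(1 + r). The larger effect therefore always has the larger weight, by value and by absolute size. Meaning against faith cannot be misranked at population level in that setting. In the simulations above, the loss in naming the largest effect is at most 4 points.
- **The inputs are unknown.** The plan calls the outcomes highly correlated but gives no value. A negative Faith weight at the pilot effect ratio needs r above about 0.65.
- **The three-arm reversal depends on the pattern assumed.** Case A reverses the arms; Case B does not.
- **Direct estimates are already planned.** The univariate contrasts estimate each component's effect for IMCP against ISP and against EUC, so it would be too strong to say that nothing else in the plan bears on the aim.

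It is also fair that the primary-aim text speaks only of contribution to the canonical function, which describes a weight correctly. The link to IMCP's impact is made only under the secondary aim.

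All of this stands, and it limits the point without removing it. Keeping the order does not protect size or sign: an 11 to 1 ratio for a 1.5 to 1 effect, or a negative weight for a component that improved, would still be reported as relative contribution. The univariate contrasts look at one component at a time. None compares components, so a difference in significance could be mistaken for a difference in effect.

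**Conclusion.** The point holds in a limited form. As written, the secondary aim labels as relative impact a quantity that does not measure it, and under the plan's own premise of high correlation that quantity can be badly distorted or carry the wrong sign. With three arms and no rule on which function to read, the weights also need not refer to either IMCP comparison.

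The size is conditional on assumed correlations and effects. With two or three truly improved components, at least one negative weight appears in 14% to 88% of simulated trials for r from 0.3 to 0.7, while the top-ranked component is usually kept about as well as with univariate differences.

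The omnibus p-value and the sample size do not depend on this. It should be fixed before analysis, as a matter for a secondary aim and for the stated reason for choosing MANOVA. It is not a threat to the primary test.

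**What to change.** 1. **Secondary aim on aspects of meaning and spiritual well-being.** Replace canonical weights as the measure of relative impact. For IMCP−ISP and IMCP−EUC, report each component's standardized mean difference with a 95% confidence interval. Add a direct test of the difference between standardized effects, for example Meaning/Peace minus Faith, with its interval.
2. **Multiplicity.** State that the FDR procedure already named in section 11.0 will be applied to this set of tests, rather than that it can be.
3. **Primary-aim text.** If weights are kept, label them descriptive, standardize them, give them separately for each IMCP contrast, and show structure coefficients beside them.

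The cost is a wording change. The data and software are the same, and most of the table comes from contrasts already planned. The downside is that a small table replaces one headline set of weights.

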The T2 (mid-intervention) assessments are made because some patients may be too sick to complete the 7-session intervention. For these patients, we will use the T2 assessment to represent the most available data on intervention effect.

Sample size and statistical power considerations:

Two important hypotheses need to be established in this trial: 1) IMCP is superior to EUC; and more importantly, 2) IMCP is superior to ISP for improving psychosocial outcomes in patients with advanced cancer. Therefore, we have based sample size considerations on sufficient statistical power to detect these two differences. We have conservatively based our sample size calculations on a 0.20 standardized mean difference in the MANOVA canonical variates between the IMCP and ISP interventions. This 0.20 difference is what Cohen would consider a —small effect size in psychosocial research (Cohen, 1992), representing subtle group differences typically observed in psychotherapy clinical trials. Cohen (1992) distilled the findings of decades of psychosocial research and arrived at a classification of a —small effect (0.20 standardized mean difference), a —medium effect (0.50 difference), and a —large effect (0.80+ difference). This —small difference is also a sensible assumption, due in part to the small group differences in some of the psychosocial outcomes in our pilot IMCP trial (Table 1, e.g., psychological distress). Thus, we planned to have a sufficiently large sample size to detect subtle differences. Overall, this conservative estimate would accommodate outcomes in psychological distress which our pilot data showed a small difference. Based on these assumptions, we would need 104 participants in each arm at post-intervention (week 7) in order to obtain a power of 0.80. Other assumptions that go into this estimation included two *a priori* contrasts (IMCP vs. EUC and IMCP vs. ISP), and a two-sided, type-I error rate of 0.01 in the MANOVA test. The statistical power calculations were obtained from the computer program G*Power version 3.1 (Faul, Erdfelder, Lang & Buchner, 2007), for a MANOVA model with six correlated outcome variables. The output of the G*Power estimate is included below.

F tests – MANOVA: Global effects

Options : Pillai V, O'Brien–Shieh Algorithm

Analysis : A priori: Compute required sample size

Input:	Effect size $f^2(V)$	= 0.20
	α err prob	= 0.01
	Power (1– β err prob)	= 0.80
	Number of groups	= 2
	Response variables	= 6

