Intent-to-treat (ITT) analysis is the gold standard in evaluating the relative efficacy of therapeutic regimes for patients assigned to different treatment arms whether or not they comply with the full treatment plan as defined in the protocol. In contrast to studies that assess clinical outcomes that are observable whether or not patients comply with therapy, it is likely in this study that patients who fail to participate in particular counseling sessions will also be missing the corresponding outcome data. Thus, examination and imputation of incomplete data will be an integral part of our ITT analysis. Data for intermediate time points might be imputable by one of several available statistical techniques. However, it is more problematic to assess outcomes for patients who essentially drop out of the study, namely, who are missing the final (and possibly preceding) evaluations. Although we shall endeavor to obtain final evaluation-time data even for patients who discontinue the counseling, but because of the likelihood that premature withdrawal is related to deteriorating physical health, we cannot rely on this and will therefore use appropriate statistical methods. One preferred approach is the Pattern-Mixture Model (Hedeker & Gibbons, 1997), which assumes that patients can be grouped into a small number of implicit cohorts with different patterns of missing data. This method models the trajectories of responses within each cohort and combines results across cohorts to make overall comparisons between treatment arms. The Pattern-Mixture Model can be relatively easily applied in practice using a publicly accessible SAS macro. This approach will handle two potential, inter-related issues, namely, intent-to-treat analysis and missing data while making a global assessment of the overall efficacy of the two types of counseling. We anticipate that the majority of patients will complete most or all of the planned sessions and the corresponding assessments. However, our pilot data suggest that there may be sufficient attrition to warrant use of the above-described approach even if drop-out rates do not differ significantly between the two treatment arms.

Missing data:

Because attrition may significantly impact the MANOVA, we will utilize several techniques for dealing with missing data (Nich & Carroll, 1997; Singer & Willett, 1991). These techniques may

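### The primary analysis is a single three-arm omnibus MANOVA; the two IMCP contrasts that the trial is meant to establish are not made analysis steps and have no multiplicity or direction rule

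*Combined protocol and SAP*

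**What the plan says.** **Primary analysis.** Under the omnibus MANOVA heading, section 11.0 says "The primary aim of this study will be evaluated in one omnibus, one-way MANOVA model". The test is framed as one "against the null hypothesis that all three randomized arms entail comparable post-intervention outcomes". The dependent variables are LAP-R, FACIT-Sp, HADS, SAHD, HAI and MQOL at week 7, and arm is the only independent variable. The description closes by saying that "the omnibus MANOVA will test whether or not the psychotherapy groups differ in all six correlated outcomes of interest".

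**Hypotheses.** The sample-size subsection names two that the trial needs to establish: "1) IMCP is superior to EUC; and more importantly, 2) IMCP is superior to ISP". Among the assumptions behind the sample size it lists two a priori "contrasts (IMCP vs. EUC and IMCP vs. ISP), and a two-sided, type-I error rate of 0.01 in the MANOVA test". The G*Power block beneath it uses Pillai V, alpha 0.01, six response variables and two groups.

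**Other places where a pairwise or outcome-level analysis might be found:**
- Secondary aims (components of meaning and of spiritual well-being, as change scores): "Univariate ANOVA contrasts will be used to compare IMCP against ISP and IMCP against EUC".
- Intent-to-treat and missing data: the pattern-mixture approach is described as "making a global assessment of the overall efficacy of the two types of counseling".
- False Discovery Rate: "analysis of the individual dependent variables can also incorporate a multiple comparisons method". No arm pair and no q are given.

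**The concern.** The hypotheses are pairwise and directional. The primary test is neither. A three-arm omnibus asks whether any arm differs from any other on any linear combination of the six outcomes. It can reject when IMCP and ISP are identical, when ISP is the better therapy, or when IMCP lies between the other two arms.

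Carrying the contrasts forward settles which pair differs but not who won, because a six-outcome contrast has no sign. The scales also run in opposite directions. Section 2.1 wants meaning, spiritual well-being and quality of life to rise, and depression, anxiety, hopelessness and desire for hastened death to fall. Sections 9.1 and 11.0 nevertheless list MQOL in the distress group.

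At stake is whether the comparison that the plan calls more important has a decision rule fixed before the data are seen. Without one, the choice of statistic, level and reading of mixed results is made afterwards.

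**Working it through.** **1. The plan's own power figure.** For two groups and p = 6, df = 6 and N − 7, and λ = N·f². With N = 104 and f² = 0.20, λ = 20.8, V = 0.20/1.20 = 0.1667, critical F(6, 97) at 0.01 = 2.9936 and power = 0.8063. All match the printed output. The powered test is therefore a two-arm, six-outcome MANOVA at 0.01, not the three-arm omnibus. (How the 104 and the effect size are used in the text is a separate matter.)

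**2. Inputs for the checks below.** From the plan: 104 per arm, three arms, six outcomes, alpha 0.01. Assumed, because the plan gives none: normal outcomes, a common correlation ρ = 0.5 (range 0.3 to 0.7), and the shift sizes.

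**3. Omnibus.** V = tr[H(H+E)⁻¹], with s = 2, m = 1.5 and n* = (309 − 6 − 1)/2 = 151. F = (305/6)·V/(2 − V) on 12 and 610 df. Simulated rejection under the null is 0.0102. For an equal shift on all six outcomes (10,000 replicates; brackets for ρ = 0.7 to 0.3):

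| Shift | IMCP = ISP, both better than EUC | Only ISP better |
|---|---|---|
| 0.2 SD | 8% (6–13) | 8% |
| 0.3 SD | 28% (19–47) | 28% |
| 0.5 SD | 90% (76–98) | 90% |

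The same holds if the shift is set by multivariate distance. At D = 0.6 the omnibus rejects 80.8% of the time when IMCP is better than both arms, 80.6% when it is worse than both, and 80.4% when it equals ISP and only EUC is worse (4,000 replicates each).

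With IMCP in the middle (ISP +0.25 SD, EUC −0.25 SD), the omnibus rejects 74%, but an IMCP contrast at 0.01 follows in only 31%.

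**4. Omnibus, then contrast at 0.01.** When IMCP equals ISP and EUC is 0.5 SD worse, IMCP vs ISP is rejected in 1.04% (simulation SE 0.05%). When only ISP is better, it is rejected in 4%, 20% and 84% at 0.2, 0.3 and 0.5 SD. Those rejections are correct, but they favour ISP, and the statistic alone does not say so.

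**5. Error control.** The nulls IMCP = EUC and IMCP = ISP together state that all three arms are equal, which is the omnibus null. Testing each contrast at 0.01 only after the omnibus rejects at 0.01 is therefore a closed procedure. The simulated familywise rate under the full null is 0.0065 (40,000 replicates). Two ungated contrasts at 0.005 each hold 0.005 + 0.005 = 0.01.

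**6. Power of a contrast.** D² = δ²·6/(1 + 5ρ). At δ = 0.5 and ρ = 0.5, D² = 0.25 × 6/3.5 = 0.4286. Then λ = (104 × 104/208)·D² = 52 × 0.4286 = 22.29.
- Ungated at 0.01: 0.865 with two-arm error (6 and 201 df), 0.871 with three-arm pooled error (6 and 304 df).
- Ungated at 0.005: 0.818 (6 and 304 df).
- Gated at 0.01 (simulation): 83–84% if IMCP beats both arms; about 73% for IMCP vs EUC if ISP lies half way.
- At 0.3 SD: 28% ungated at 0.01, 21% ungated at 0.005, 20% gated with IMCP better than both arms.

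**The case against.** **The contrasts are not absent.** The sample-size text fixes both pairs in advance, and the two-group Pillai run at 0.01 implies a statistic and a level for each. A reader might infer that the plan nowhere says how IMCP and ISP would be compared. That goes too far. What is missing is the step that makes these contrasts part of the primary analysis, the error control between them, and the sign rule.

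**The 90% is not a false-positive rate.** It is power to detect a difference that exists. A reader might infer that the plan takes a significant omnibus to mean that IMCP beats ISP, and so would wrongly claim superiority about 90% of the time. The documents never say this, and the omnibus is a fair test of the broad primary aim in section 2.1, which is to compare three arms. On the natural reading of omnibus then contrast, false rejection of IMCP vs ISP is about 1%.

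**Direction is not wholly missing.** Section 2.1 says what should rise and what should fall, and two-sided results are usually read with the sign of the means. This answers the case where all six outcomes agree. It leaves the mixed case open, which is where a multivariate test needs a rule.

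**The remedy involves choices.** A gate, a particular q and a particular sign rule do not follow from the documents. This stands, so they are offered below as options.

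**Conclusion.** The point holds as a gap between the stated hypotheses and the stated primary test. Followed as written, the primary analysis cannot tell whether IMCP is superior to ISP: at 0.5 SD it rejects about 90% of the time whether IMCP equals ISP or ISP alone is better (76–98% for correlations of 0.7 to 0.3). No other part of section 11.0 closes the gap, since the only written IMCP contrasts serve a secondary aim and the outcome-level analysis is optional.

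The rates rest on assumed normality, equal correlations and equal shifts. The structural conclusion does not: an omnibus test is indifferent to which arm differs and in which direction. It should be fixed before analysis. The description of the test as covering a difference in all six outcomes is a minor wording error, because a 0.5 SD shift on only two outcomes is enough for rejection in over 99% of simulated trials at correlation 0.5.

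**What to change.** In the primary-aim paragraph of section 11.0:

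1. Make IMCP vs EUC and IMCP vs ISP, as six-outcome MANOVA contrasts on the week 7 primary outcomes, the basis of any superiority conclusion.
2. Hold overall error at 0.01 by one named route: each contrast at 0.01 only if the omnibus rejects at 0.01, or both ungated at 0.005.
3. State how direction is read. Code all six scales so that higher is better, and call a significant contrast superiority only when the outcome-level results favour IMCP. One option is to require at least one outcome favouring IMCP after the plan's Benjamini-Hochberg procedure at a pre-stated q, and none significantly favouring the comparator. Otherwise report a difference only.
4. Reword the test as detecting a difference on at least one linear combination of the six outcomes.

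**Cost.** A few sentences, with the same data and software. Power falls from about 87% (ungated at 0.01, 0.5 SD, correlation 0.5) to 83–84% with the gate if IMCP beats both arms, to about 73% for IMCP vs EUC with the gate if ISP lies half way, or to about 82% with two tests at 0.005.

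The sign rule in item 3, tried with the gate and an assumed q of 0.05, costs almost nothing when all outcomes move together. With 0.5 SD on two outcomes only, it lowers the claim of IMCP over EUC from 99% to 91%. It limits mixed-effect claims but does not remove them: with +0.3 SD on three outcomes and −0.3 SD on three, superiority is still claimed about 24% of the time (18–29% for correlations 0.3 to 0.7). A stricter rule may be preferred.
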